6.5. Day 28 Follow up Assessment (±5 Days)

The following evaluations are to be completed if this visit is conducted in person. For participants who have been discharged from hospital, the final evaluation can be made by phone. Only AE and concomitant medication and ordinal scale (if discharged on or after Day 14) review are to be completed if visit is conducted by phone.

- Physical examination and vital signs (heart rate, temperature, blood pressure)

- Documentation of respiratory status:

Respiratory rate

- Oxygen supplementation: room air, low flow O₂ (L/min and %), high flow O₂ (L/min and %), CPAP/BIPAP (FiO₂ or %), mechanical ventilation (FiO₂ or %), ECMO

Oxygenation: SpO₂ or PaO₂

Radiographic findings (if available)

- Review AEs and document concomitant medications
- Review the Ordinal Scale (Section 6.9). If subject was not discharged by Day 14, any change in category and the date of any change in category from Day 14 to discharge (or Day 28) should be recorded

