3.8.2. Analysis Visit Windows

Participant visits might not occur on protocol-specified days. Therefore, for the purposes of analysis, observations will be assigned to analysis windows. The study day as defined in Section [3.8.1](#) will be used when data are summarized by visit.

Vital signs were to be collected daily; therefore, windows are not assigned, and results will be summarized for each Study Day, except for Study Day 28. For Study Day 28, the nominal day is Study Day 28, the lower limit is Study Day 15 and there is no upper limit.

Ordinal scale results were to be recorded prior to dosing on Study Day 1. The worst result for each day from Day 1 (after first dose) through the earliest of discharge date or Day 14 was to be recorded. For participants who were discharged after Day 14, changes in score category were to be recorded each day from Day 15 to the earliest of discharge date or Day 28. For the ordinal scale, baseline is defined as the value recorded prior to dosing, or the last value obtained prior to the first dose date if the predose value was not recorded on the day of dosing. Results will be summarized for each Study Day without windows. If more than one result was reported on the same day, the worst result will be selected.

The analysis windows for hematology and chemistry laboratory parameters are presented in [Table 3-1](#).

Table 3-1. Analysis Windows for Hematology and Chemistry Laboratory Tests (hemoglobin, hematocrit, platelet count, WBC, ALT, AST, total bilirubin, glucose, serum creatinine, and creatinine clearance)

Visit ID	Nominal Day	Lower Limit	Upper Limit
Baseline	1		1 (predose)*
Day 3	3	1 (postdose)*	3
Day 5	5	4	6
Day 8	8	7	8
Day 10	10	9	11
Day 14	14	12	15
Post Day 14**	28	16	

* For Baseline, the upper limit includes values collected at or prior to the first dose date/time. For Day 3, the lower limit includes values collected after the first dose date/time on Day 1.

** Post Day 14 laboratory values will be considered for treatment emergent laboratory presentations only.

3.8.3. Selection of Data in the Event of Multiple Records for an Analysis Visit Day

Depending on the statistical analysis method, single values may be required for each Study Day or analysis window. For example, change from baseline by visit usually requires a single value, whereas a time-to-event analysis does not require 1 value per Study Day or analysis window.

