6.2. Efficacy Endpoints of Interest

Efficacy endpoints of interest include endpoints based on clinical status assessed by a 7-point ordinal scale. The endpoint will be derived by combining the available death, hospital discharge alive and ordinal scale assessment reported by the site, where death supersedes discharge alive and discharge alive supersedes the ordinal scale score reported by the site.

Sites were instructed to report the worst ordinal scale category for each day. Therefore, the ordinal scale result on the day the participant was discharged alive does not necessarily reflect Not hospitalized (7). The definition of clinical status based on the 7-point ordinal scale is defined as follows:

- If a participant dies while hospitalized (as recorded on the Death eCRF and Hospitalization eCRF), the endpoint on the day of death and all subsequent days through Day 28 will be set to Death (1)
- If the participant is discharged alive, the endpoint on the day of discharge alive and all subsequent days through Day 28 will be set to Not hospitalized (7)
- If the participant is discharged alive and dies on the same day or a later day (as recorded on the Death eCRF and Hospitalization eCRF), the endpoint on the day of discharge alive and all subsequent days until the day of death will be set to Not hospitalized (7). On the day of death and all subsequent days through Day 28, the endpoint will be set to Death (1),

Every effort will be made to obtain clinical status data for all participants prior to discharge alive. The last known clinical status will be used for days with missing clinical status (eg, where the reason for Hospital Discharge is not “Discharged Alive” and the participant has not died). All post-baseline days with missing ordinal scale score, from Day 2 to Day 14 and Day 28, will use the previous last known clinical status.

Efficacy endpoints of interest include

- Clinical status on Days 1 to 14, Day 28 and last available assessment
- Change in clinical status on Days 5, 7, 11, 14, 28, and last available assessment
- Time to clinical improvement (days): Clinical improvement is defined as a ≥ 2 -point improvement from baseline clinical status or discharged alive on the 7-point ordinal scale using the definition specified above.

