6.2.1. Analysis of Efficacy Endpoints of Interest

The number and percentage of participants in each clinical status category for each day from Baseline through Day 14 and at Day 28 and using the last available assessment will be summarized by group. These results will be summarized using (1) the clinical status definition in Section 6.2 and (2) with the definition specified in Section 6.2 but excluding days with missing ordinal scale score not due to death or discharge alive. In addition, stacked bar charts by study day (Baseline through Day 14 and at Day 28) will be produced by group using the definition specified in Section 6.2.

The number and percentage of participants in each clinical status category for each day from Baseline through Day 14 and at Day 28 and last available assessment will be summarized within each subgroup defined in Section 3.4.1.

The change from baseline in clinical status category on Days 5, 7, 11, 14, 28 and last available assessment will be summarized by group using descriptive statistics.

Number of days of oxygen support status modes (invasive mechanical ventilation, high flow oxygen, low flow oxygen) will be calculated as the number of days oxygen support was reported on the 7-point ordinal scale eCRF through death, discharge alive, or Day 14 and presented for each group using descriptive statistics.

A shift table of baseline oxygen support status (death, invasive mechanical ventilation, high flow oxygen, low flow oxygen, room air, discharge alive) to Days 5, 7, 11, 14, 28 and the last available status will be provided for each group.

Duration of hospitalization will be calculated only for participants who are discharged alive on or prior to Day 28 and will be summarized for each group using descriptive statistics.

All-cause mortality will be estimated for each group using the Kaplan-Meier product limit method with all available data. Participants who did not die will be censored at the last study day.

Days to clinical improvement and days to recovery will be estimated for each group using a competing risk analysis approach, with death as the competing risk. Participants without recovery will be censored on the day of the last non-missing ordinal scale assessment.

Forest plots by subgroup will be presented for all-cause mortality Kaplan-Meier estimates on Day 28 and cumulative incidence of recovery on Day 28.

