Appendix 1. Study Procedures Table

	Screening	Baseline / Day 1 ^b	Day 2	Day 3	Day 4	Day 5	Days 6 and 7	Day 8	Day 9	Day 10	Days 11, 12 and 13	Day 14	Day 28 ^c Follow-up (±5 days)
Written Informed Consent	X												
Medical History	X												
Physical Examination	X	X	X	X	X	X	X	X	X	X	X	X	X
Height	X												
Vital Signs ^a	X	X	X	X	X	X	X	X	X	X	X	X	X
Study Laboratory Testing	X	X		X		X		X		X		X	
Respiratory Status	X	X	X	X	X	X	X	X	X	X	X	X	X
Ordinal Scale		X	X	X	X	X	X	X	X	X	X	X	X
Pregnancy Test	X												

CCI

RDV Dosing for Group 1		X	X	X	X	X							
RDV Dosing for Group 2		X	X	X	X	X	X	X	X	X			
Adverse Events	X	X	X	X	X	X	X	X	X	X	X	X	X
Concomitant Medications	X	X	X	X	X	X	X	X	X	X	X	X	X

- a Includes heart rate, respiratory rate, temperature, blood pressure, SpO₂ at rest, and body weight. Body weight collected on screening and Day 1 and otherwise if available.
- b Assessments need not be repeated if performed the same calendar day as screening procedures.; data collection other than adverse events should stop Day 14 or discharge whichever is earlier.
- c Day 28 evaluations completed if the visit is conducted in person. Only AEs, ordinal scale, and concomitant medication review completed if visit conducted by phone.

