Hematology	Hemoglobin (g/dL)	1
Hematology	Hematocrit (%)	1
Hematology	Platelet count (x10 ⁹ /L)	0
Hematology	WBC (x10 ⁹ /L)	2
Chemistry	ALT (U/L)	0
Chemistry	AST (U/L)	0
Chemistry	Total bilirubin (mg/dL)	2
Chemistry	Glucose (mg/dL)	0
Chemistry	Serum creatinine (mg/dL)	2
Chemistry	Creatinine Clearance by Cockcroft Gault (mL/min)	1

Standard deviation and standard error will be reported to one more significant decimal place than the raw measurement.

Mean, median, minimum, Q1, Q3, and maximum will be reported to the same number of decimal places of the raw measurements.

Exceptions may be considered; for example, if more than 4 significant digits are provided for the measurement.

- 14) Last dose date is not expected to be missing. However, if last dose date is missing, it will be imputed using the maximum of non-missing, non-zero dose, study drug start and stop dates.
- 15) Incomplete death dates will be imputed as the maximum of the study drug start dates (lasfdt), study drug end dates (lasldt), clinic visit dates (lvis28dt), laboratory visit dates (llab28dt), including the 28-day follow-up visit date plus 1, ie dthdt
 $\max(\text{lasfdt}, \text{lasldt}, \text{lvis28dt}, \text{llab28dt}) + 1$.
- 16) Ordinal scale and oxygen support status

The oxygen support status is derived from the ordinal scale:

Ordinal Scale		Oxygen Support Status
1	Death	Death
2	Hospitalized, on invasive mechanical ventilation or ECMO	Invasive Mechanical Ventilation
3	Hospitalized, on non invasive ventilation or high flow oxygen devices	High Flow Oxygen
4	Hospitalized, requiring low flow supplemental oxygen	Low Flow Oxygen
5	Hospitalized, not requiring supplemental oxygen requiring ongoing medical care (COVID 19 related or otherwise)	Room Air
6	Hospitalized, not requiring supplemental oxygen no longer requires ongoing medical care (other than per protocol RDV administration)	Room Air
7	Not hospitalized	Discharge

17) Censoring rules

Time to death: participants are censored at the last known date alive (last study day)

Time to ≥ 2 -point improvement, time to ≥ 1 -point improvement, time to recovery; if a participant does not experience the event of interest and does not die, the participant is censored at the last non-missing ordinal scale assessment date.

18) Graded Laboratory Abnormalities Summary

The following labels will be used for laboratory abnormalities and Grade 3 or 4 laboratory abnormalities summary tables and listings:

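### Censoring non-recovered participants at their last ordinal record would overstate Part B cumulative recovery and improvement wherever an unchanged inpatient lacks a usable Day 28 score

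*SAP*

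**What the plan says.** **Censoring.** SAP Section 6.2.1 states: "Participants without recovery will be censored on the day of the last non-missing ordinal scale assessment". SAP Appendix 2, item 17, applies the rule to recovery and to both the 1-point and 2-point improvement endpoints: where there is neither event nor death, "the participant is censored at the last non-missing ordinal scale assessment date". The same item censors time to death at the last date known alive. The estimator is cumulative incidence with death as the competing risk, and Day 28 cumulative recovery is shown in subgroup forest plots.

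**Recording after Day 14.** For participants not discharged by Day 14, Protocol Section 6.5 asks that "any change in category and the date of any change in category from Day 14 to discharge (or Day 28) should be recorded". For participants whose discharge came later than Day 14, SAP Section 3.8.2 describes the same practice: "changes in score category were to be recorded each day from Day 15 to the earliest of discharge date or Day 28". Neither asks for a daily score on Days 15 to 27.

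**Day 28.** Protocol Section 6.5 and both schedules of procedures include an ordinal review at the Day 28 visit (±5 days), also when it is done by phone: "Only AEs, ordinal scale, and concomitant medication review completed if visit conducted by phone". Footnote b of the SAP schedule, however, says that "data collection other than adverse events should stop Day 14 or discharge whichever is earlier", and the protocol's footnote b is to the same effect. SAP Section 6.2 provides for missing scores, Day 28 included: "All post-baseline days with missing ordinal scale score, from Day 2 to Day 14 and Day 28" take the last known status.

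**Events.** Under SAP Section 6.2, discharge alive sets the status to 7 and death sets it to 1, using the Hospitalization and Death eCRFs. Neither needs an ordinal entry.

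**The concern.** Events and non-events are followed through different data streams. A discharge on Day 22 counts on Day 22 whether or not anyone scored the participant. A participant still in hospital and unchanged on Day 22 generates no entry, so that person's follow-up ends at the last score on file. If no score is entered at Day 28, that is Day 14, or the date of the last category change if later.

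The time of leaving the risk set then depends on the outcome. Cumulative incidence assumes that people censored at a given time go on to recover or die like those still followed. Here the people censored are those who did neither. Recovery and death curves are both pushed up, and in the limit, where every non-event is censored at Day 14, they are forced to sum to 100% by Day 28.

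At stake are the competing-risk estimates of days to recovery and days to improvement, and the Day 28 recovery forest plots. Groups with more people still in hospital at Day 28 are likely to be distorted more, so comparisons across subgroups could be affected as well as the levels.

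**Working it through.** The documents give no recovery rate for Part B and no rate of missing Day 28 scores, so there is no figure in the plan to reproduce. Everything below is conditional on assumed rates.

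**Formula.** Let R be the percentage recovered by Day 14, A the percentage alive and not recovered at Day 14, r the percentage recovering on Days 15 to 28, and n the percentage with neither event by Day 28. Let q be the share of n with no ordinal record after Day 14. Those are censored at Day 14 and the rest at Day 28. With no other censoring, the estimated Day 28 cumulative recovery is

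R + A × r / (A − q × n).

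At q = 0 this is R + r, the true value.

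**Case 1: 35% recover, 30% die, 35% still in hospital, event times uniform over Days 2 to 28 (27 days); all assumed.**
- R = 35 × 13/27 = 16.85; deaths by Day 14 = 30 × 13/27 = 14.44; A = 100 − 16.85 − 14.44 = 68.70 (from unrounded values); r = 35 × 14/27 = 18.15; n = 35.
- q = 10%: 16.85 + 68.70 × 18.15/65.20 = 36.0%
- q = 25%: 16.85 + 68.70 × 18.15/59.95 = 37.6%
- q = 50%: 16.85 + 68.70 × 18.15/51.20 = 41.2%

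**Case 2: Extension-type.** The SAP's planning distribution at Day 14 (Section 1.3, Part A Treatment Group 1) gives R = 20 + 38 = 58 in categories 6 and 7, with 2 dead, so A = 40. Assume that half of the 40 recover later and a tenth die: r = 20, n = 16.
- q = 25%: 58 + 40 × 20/36 = 80.2%, against a true 78.0%
- q = 50%: 58 + 40 × 20/32 = 83.0%
- q = 100%: 58 + 40 × 20/24 = 91.3%

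**Case 3: ventilated-type, all rates assumed.** R = 20, dead 20, A = 60; of these 30% recover later and 15% die: r = 18, n = 33.
- q = 25%: 20 + 60 × 18/51.75 = 40.9%, against a true 38.0%
- q = 50%: 20 + 60 × 18/43.5 = 44.8%
- q = 100%: 20 + 60 × 18/27 = 60.0%

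**Timing.** If Case 1 event times are front-loaded instead (exponential decay, scale 8 days, assumed), q = 10% gives 35.5%.

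**Visit window.** Suppose q = 0 and Day 28 visits fall evenly on Days 23 to 33. Cumulative incidence computed day by day for the Case 1 rates gives:
- non-events censored at the visit, but events still counted to Day 28: about 37.0%
- follow-up ending at the visit for everyone: 35.0%, no bias
- deaths after the visit counted, discharges not: 34.8%
- first variant with front-loaded times: 35.4%

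**The case against.** The strongest reply is that the ordinal scale is itself a Day 28 item, by phone if need be. Anyone with that review is censored at the visit and not at Day 14. This stands: change-only recording does not by itself censor every non-recovered participant early, and at q = 0 the Day 14 bias is nil. What remains is that footnote b says to stop non-AE collection at Day 14 or discharge, SAP Section 3.8.2 describes only change records after Day 14, and Section 6.2 provides for missing Day 28 scores.

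A reader might infer that the ±5-day window biases the estimate even with full attendance. The documents do not establish this. It requires discharges after an early visit to be captured up to Day 28 while non-events stop at the visit. The request to record changes to Day 28 points that way, but no text says how long discharges are tracked after an early visit. If follow-up ends at the visit for everyone, the bias is zero.

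A reader might also see a contradiction with Section 6.2, which carries status forward to Day 28. That is not shown. Carry-forward fills a status endpoint, and a censoring date is a separate rule. What is missing is a statement of whether a carried-forward status counts as a non-missing assessment.

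Two further points stand. The rates are assumed, and uniform timing places many events late, which enlarges the bias. And presence in hospital does not prove non-recovery, because category 6 is an inpatient category that counts as recovery.

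**Conclusion.** The concern holds in conditional form. For participants still in hospital and unchanged who have no usable Day 28 score, the stated rule makes censoring depend on the outcome and overstates cumulative recovery and improvement. Under the Case 1 assumptions the overstatement is about 1, 3 and 6 percentage points when 10%, 25% and 50% of remaining inpatients lack a later record. Cases 2 and 3 give about 2 to 3 points at 25% and 5 to 7 points at 50%. The true share is unknown. The visit window could add about 2 points under Case 1, but only if events are captured beyond an early visit.

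The reach is limited. SAP Section 3.3 rules out formal testing in Part B, so this is bias in descriptive estimates and not a type I error problem. The fixed-day percentages with improvement or recovery do not use the censoring rule and are unaffected, provided that carried-forward status keeps non-events in the denominator. The Part A primary analysis is not touched. The point still merits correction, because estimation is all that Part B delivers and the remedy is small.

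**What to change.** In SAP Section 6.2.1 and Appendix 2, item 17:

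1. Censor participants known to be alive, still in hospital and with no recorded change to a qualifying category at Day 28, or at the last date this is known if earlier. Require both conditions, since being in hospital alone does not exclude recovery to category 6.
2. Apply the same Day 28 cut-off to events, and state whether the absence of a discharge or death entry through Day 28 counts as known to be in hospital. Without that statement the visit-window question stays open.
3. State that the status carried forward under Section 6.2 supports this censoring date.
4. Reconcile footnote b of the schedules with the Day 28 ordinal item.
5. Report, by group, how many participants without the event lack a Day 28 ordinal record.

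The cost is mainly SAP wording and a change to one derivation, using the Hospitalization and Death eCRFs that the SAP already cites. The documents do not show the layout of the Hospitalization eCRF, so whether it holds a last-known inpatient date for people not yet discharged must be checked first. A change after SAP finalization would be documented in the CSR, as SAP Section 1 provides.

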Appendix 3. Renal Events

An adverse event record will be flagged as a renal event if its MedDRA PT is included in this pre-specified PT list, which includes all PTs from the broad and narrow search of the acute renal failure SMQ under MedDRA v22.1 provided by Gilead GLPS (search name: Acute Renal Failure (SMQ)) and reviewed by Gilead medical monitors.

SMQ Source	Preferred Term
Acute Renal Failure (SMQ)	Albuminuria
	Anuria
	Azotaemia
	Blood creatinine abnormal
	Blood creatinine increased
	Blood urea abnormal
	Blood urea increased
	Creatinine renal clearance decreased
	Glomerular filtration rate abnormal
	Glomerular filtration rate decreased
	Haemodialysis
	Nephritis
	Nephropathy toxic
	Oliguria
	Peritoneal dialysis
	Proteinuria
	Renal failure
	Renal failure neonatal
	Renal transplant
	Renal tubular disorder
	Renal tubular necrosis
	Urea renal clearance decreased
	Tubulointerstitial nephritis
	Oedema due to renal disease
	Renal impairment neonatal
	Neonatal anuria
	Renal tubular dysfunction
	Blood urea nitrogen/creatinine ratio increased
Haemofiltration	

SMQ Source	Preferred Term
	Protein urine present
	Creatinine urine decreased
	Urine output decreased
	Dialysis
	Renal function test abnormal
	Renal impairment
	Hypercreatininaemia
	Continuous haemodiafiltration
	Creatinine renal clearance abnormal
	Kidney injury molecule-1
	Acute kidney injury
	Acute phosphate nephropathy
	Creatinine urine abnormal
	Crystal nephropathy
	Prerenal failure
	Intradialytic parenteral nutrition
	Fractional excretion of sodium
	Hyponatriuria
	Renal tubular injury
	Foetal renal impairment
	Subacute kidney injury
	Neutrophil gelatinase-associated lipocalin increased

Appendix 4. Hepatic Events

An adverse event record will be flagged as a hepatic event if its MedDRA PT is included in this pre-specified PT list, which includes the following 152 PTs for acute and non-infectious liver events under MedDRA v22.1 provided by Gilead GLPS (search name: Acute and non-infectious liver events_simple) and reviewed by Gilead medical monitors.

Search Term	Preferred Term
Acute and Non-infectious Liver Events	5'nucleotidase increased
	Acute hepatic failure
	Alanine aminotransferase abnormal
	Alanine aminotransferase increased
	Ammonia abnormal
	Ammonia increased
	Aspartate aminotransferase abnormal
	Aspartate aminotransferase increased
	Asterixis
	Autoimmune hepatitis
	Bilirubin conjugated increased
	Biopsy liver abnormal
	Blood bilirubin increased
	Blood bilirubin unconjugated increased
	Blood cholinesterase abnormal
	Blood cholinesterase decreased
	Blood fibrinogen abnormal
	Blood fibrinogen decreased
	Blood thrombin abnormal
	Blood thrombin decreased
	Blood thromboplastin abnormal
	Blood thromboplastin decreased
	Bromsulphthalein test abnormal
	Cholestasis
	Coagulation factor decreased
	Coagulation factor IX level decreased
	Coagulation factor V level decreased
	Coagulation factor VII level decreased
	Coagulation factor X level decreased

Search Term	Preferred Term
	Coma hepatic
	Gamma-glutamyl transferase abnormal
	Gamma-glutamyl transferase increased
	Hepaplastin abnormal
	Hepaplastin decreased
	Hepatic encephalopathy
	Hepatic failure
	Hepatic function abnormal
	Hepatic necrosis
	Hepatic pain
	Hepatitis
	Hepatitis acute
	Hepatitis cholestatic
	Hepatitis fulminant
	Hepatitis toxic
	Hepatocellular injury
	Hepatomegaly
	Hepatorenal failure
	Hepatorenal syndrome
	Hepatosplenomegaly
	Hepatotoxicity
	Hyperammonaemia
	Hyperbilirubinaemia
	Hypocoagulable state
	Hypoprothrombinaemia
	Icterus index increased
	International normalised ratio abnormal
	International normalised ratio increased
	Jaundice
	Jaundice cholestatic
	Jaundice hepatocellular
	Leucine aminopeptidase increased
	Liver disorder

Search Term	Preferred Term
	Liver function test abnormal
	Liver tenderness
	Protein C decreased
	Prothrombin level abnormal
	Prothrombin level decreased
	Prothrombin time abnormal
	Prothrombin time prolonged
	Prothrombin time ratio increased
	Ultrasound liver abnormal
	Yellow skin
	Cholaemia
	Glutamate dehydrogenase increased
	Antithrombin III decreased
	Urine bilirubin increased
	Protein S decreased
	Hypofibrinogenaemia
	Thrombin time abnormal
	Guanase increased
	Bile output decreased
	Bile output abnormal
	Thrombin time prolonged
	Protein S abnormal
	Hepatopulmonary syndrome
	Foetor hepaticus
	Perihepatic discomfort
	Transaminases increased
	X-ray hepatobiliary abnormal
	Subacute hepatic failure
	Ocular icterus
	Blood bilirubin abnormal
	Hypothrombinaemia
	Hypothromboplastinaemia
	Blood alkaline phosphatase increased

Search Term	Preferred Term
	Blood alkaline phosphatase abnormal
	Galactose elimination capacity test abnormal
	Galactose elimination capacity test decreased
	Hepatic enzyme increased
	Bilirubin excretion disorder
	Coagulation factor IX level abnormal
	Coagulation factor V level abnormal
	Coagulation factor VII level abnormal
	Coagulation factor X level abnormal
	Prothrombin time ratio abnormal
	Liver scan abnormal
	Hepatobiliary disease
	Hepatic enzyme abnormal
	Transaminases abnormal
	Cholestatic pruritus
	Total bile acids increased
	Hepatic infiltration eosinophilic
	Mitochondrial aspartate aminotransferase increased
	Hepatobiliary scan abnormal
	Hepatic encephalopathy prophylaxis
	Mixed liver injury
	Molar ratio of total branched-chain amino acid to tyrosine
	Liver injury
	Bilirubin conjugated abnormal
	Cholestatic liver injury
	Hypertransaminasaemia
	Child-Pugh-Turcotte score increased
	Acquired protein S deficiency
	Urobilinogen urine increased
	Acute yellow liver atrophy
	Allergic hepatitis
	Deficiency of bile secretion
	Drug-induced liver injury

Search Term	Preferred Term
	Parenteral nutrition associated liver disease
	Acquired antithrombin III deficiency
	Hyperfibrinolysis
	Portal tract inflammation
	Liver palpable
	Minimal hepatic encephalopathy
	Hepatic hypertrophy
	Liver dialysis
	Child-Pugh-Turcotte score abnormal
	Model for end stage liver disease score abnormal
	Model for end stage liver disease score increased
	Acute on chronic liver failure
	Bilirubin urine present
	Anti factor X activity abnormal
	Anti factor X activity increased
	Liver function test increased
	Computerised tomogram liver abnormal
	Immune-mediated hepatitis
	Hepatic lymphocytic infiltration
	Acquired factor VIII deficiency
	Acquired factor XI deficiency
	Acquired factor IX deficiency
	AST/ALT ratio abnormal
	Magnetic resonance imaging liver abnormal

GS-US-540-5773_Part_B_SAP

ELECTRONIC SIGNATURES

Signed by	Meaning of Signature	Server Date (dd-MMM- yyyy hh:mm:ss)
PPD	Biostatistics eSigned	24-Sep-2020 16:00:10
PPD	Clinical Research eSigned	25-Sep-2020 05:27:22
